5. PROJECT DESIGN

5.1 Type of research and general project design

This project has an effectiveness-implementation hybrid design.

1) Effectiveness study:

The effectiveness is evaluated by a cluster-randomised controlled trial of an interprofessionnal quality-circle module on deprescribing. The unit of analysis for this study is the NH; all data will be aggregated at the NH level, and no data regarding individual residents will be provided to the investigators.

Participating NHs will be randomised between intervention and control groups (ratio 1:1), clustered according to their responsible physician. NHs allocated to the intervention group will hold a QC session on the topic of deprescribing and will produce a local consensus on how to deprescribe specific therapeutic classes in the NH.

2) Implementation study:

The implementation study is based on a mixed method approach combining quantitative and qualitative evaluation of the implementation strategies of the deprescribing-specific interdisciplinary quality circle module as well as the resulting deprescribing consensus. Only the intervention group will be concerned by most of the evaluations.

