5.2 Recruitment and Screening

Participants will be recruited among the NHs currently taking part in their respective cantonal pharmaceutical assistance programmes. The investigators have direct access to these NHs and their respective pharmacists through their mandate for the monitoring of these two programmes.

All NHs of Vaud and Fribourg with a mainly geriatric mission and that have been part of the programmes for more than a year will be offered the possibility to participate in this study by direct mailing from the investigators. Pharmacists providing the pharmaceutical assistance for these NHs will also be directly informed, and nurses and physicians will be contacted through their respective professional societies. The approval of all partners (NH direction, head nurse, responsible physician and pharmacist) will be required for enrolment (see Annex 2 for agreement to participate).

In case of insufficient recruitment, a second recruitment round will take place in 2018. The NHs agreeing to take part in this second round will be randomised as described in section 5.3, page 13; those allocated to the intervention group will then hold a QC session between December 2018 and January 2019. Data of the two recruitment rounds will be pooled for analysis (see section 8.2, page 18).

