In the two months following course completion, every NH in the intervention group will hold a QC session prepared by the pharmacist based on the course. This session will address both generalities about polypharmacy, PIMs and deprescribing, and an in-depth discussion of the guidelines for deprescribing therapeutic classes selected by the pharmacist on the basis of their use in the NH. It is to be noted that the data necessary to select the specific therapeutic classes discussed during the session are both routinely collected and analysed by the NHs' pharmacists, due to their participation in their respective cantonal pharmaceutical assistance programme.

At the end of the session, participants will be required to build a consensus for deprescribing specific therapeutic classes in the NHs. This consensus will then be enacted by the care team, according to their best clinical knowledge. In addition, the participants will be encouraged to think about the strategies to implement each deprescribing measures chosen for the consensus. Physicians will retain complete control over therapeutic choices for individual residents, including the choice to enact the consensus or not.

In addition, the pharmacist will be required to send the consensus with strategies to the other participants two weeks after the session, to include a specific chapter about deprescribing in their PAP annual report for 2017 and to discuss the implementation of the consensus during the presentation of this report to the NH team.

All consensus and implementation strategies chosen by the participating NHs will be collected by the investigators, compiled and, after anonymization, communicated to the participants during the first trimester of 2018.

Data collection:

Assessment of this project's outcomes will be made using anonymised data, provided by the CPC monitoring team. These data will comprise, for every NH and every year:

- Mission of the NH (geriatric, psycho-geriatric, or mixed);
- Number of beds in the NH;
- Mean age of NH residents;
- Gender repartition of the residents;
- Total number of days spent at the NH;

- Total number of days sent in the hospital;
- Total number of deaths in the NH;
- Designation, pharmacode, number of boxes and total cost of every drug used in the NH during the year.

Some data will be collected directly in the NHs; these data will be aggregated at the NH level:

- Total number of falls in the NH;
- Total number of residents having fallen, if available;

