5.4 Methods of minimising bias

To account for the other influences on the prescribing practices of physicians, a controlled design has been chosen. Thus, external influence from medical literature, expert opinions, treatment guidelines or other sources should equally impact NHs in the intervention and control groups.

Randomisation will increase the likelihood that the characteristics of participating NHs are similar between the two groups. To account for the fact that some physicians are responsible for more than one NH, thus allowing for "bleeding" of the intervention between the two groups, randomisation will be clustered at the physician level (see section 5.3, page 13 for details).

Previous discussions with the prospective participants and their professional associations show that there is a great interest for deprescribing among partners. We fear that a purely controlled design will prevent the participation of some of the most interested NHs, thus minimising the effect of the intervention. To reduce this risk, we will offer the possibility to participants randomized to the control group to enact the intervention one year after the start of the study. At this point, all NH in the intervention group will have submitted to the intervention and its effects will have full deployed.

Finally, assessments of the study outcomes will be conducted while maintaining allocation blinding, ensuring that no analysis bias occurs.

Given that the unit of analysis is the NH, the risk of loss to follow-up is deemed inexistent. Data collection will take place in the same way as it already routinely does in a satisfactory way, thus reducing the risk of missing data.

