8.3 Planned analysis

Descriptive statistics

Participating NH will be described, by group, in terms of number of beds, mean age of residents, mission (geriatric, psycho-geriatric or mixed), and number of nurses, physicians and pharmacists. Each implementation outcome (list available in Annex 1) will be presented with a suited summative data.

Inferential statistics

The main outcome is the difference in the overall proportion of PIMs used in the NH 12 months after intervention, relative to baseline. The primary analysis will test the difference in the overall proportion of PIMs between the intervention and control groups using a generalised linear regression model, taking the difference in overall proportion of PIMs at 12 months as the dependant variable, and the group allocation (binary variable) and baseline overall proportion of PIMs as independent variables (two-sided α = 0.05). The analysis will be made immediately after the completion of follow-up data collection.

The same analysis will be carried out for the co-primary outcome, with the overall number of potentially inappropriate DDD at 12 months as dependent variable, adjusted for baseline value, taking into account the group allocation.

Generalised linear models will also be used to assess differences in secondary outcomes between the two groups will be tested with the same method as the primary outcome, taking the baseline value and the group allocation as the independent variables, with two-sided $\alpha = 0.05$. If enough supplementary data on falls and hospitalisations are available (see section 7.3 page 19), they will be analysed as the number of falls, respectively the number of hospital days, per mean resident and per year.

All analyses will be made using the Stata statistical package (StataCorp LP, College Station, TX, USA).

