8.3.1 Datasets to be analysed

All retrospective data collected will be used for the main analysis. If some NH allocated to the intervention group do not hold the QC session but provide their data, they will be included in the analysis. The statistician performing the analysis will be blinded to the allocation; groups will be identified as A and B.

Subgroups analysis will be made, both for the primary and secondary outcomes, for the following subgroups:

- NH of Vaud;
- NH of Fribourg;
- NH with a geriatric mission;
- NH with a psychogeriatric mission;
- NH having held the QC session.

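### The protocol's subgroup of nursing homes that held the QC session has no control arm, so the planned group effect cannot be estimated in it

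*Protocol*

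**What the plan says.** Protocol section 8.3.1 announces: "Subgroups analysis will be made, both for the primary and secondary outcomes, for the following subgroups". The list has two cantons, two missions and, last, "NH having held the QC session". No comparator and no separate model is given for any of them. The same section foresees non-adherence: "If some NH allocated to the intervention group do not hold the QC session but provide their data, they will be included in the analysis".

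Only one arm holds the session. Section 5.1: "NHs allocated to the intervention group will hold a QC session on the topic of deprescribing". Section 5.3: "every NH in the intervention group will hold a QC session prepared by the pharmacist based on the course". For a second recruitment round, section 5.2: "those allocated to the intervention group will then hold a QC session between December 2018 and January 2019". Controls have access later (section 5.4): "we will offer the possibility to participants randomized to the control group to enact the intervention one year after the start of the study".

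Section 8.3 models the 12-month change on group allocation and the baseline value. The SAP (Inferential analysis) follows intention to treat and expects every NH to comply with its allocation. It describes no subgroup or per-protocol analysis, and protocol section 8.3.3 plans no ancillary analysis.

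**The concern.** Canton and mission are fixed before randomisation, and both arms occur at each level. Holding the session is different: it happens after randomisation and, by design, in one arm only. The planned two-group analysis therefore has nothing to compare within this subgroup.

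An analyst who meets the line at reporting time will have to improvise. The obvious improvisation sets session holders against all controls. That filters the intervention arm by what its teams did after allocation and leaves the control arm unfiltered, so the comparison is no longer protected by randomisation. It could still be read as the effect of the module where it was actually delivered, which is a figure that readers of a hybrid effectiveness-implementation trial will look for.

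**Working it through.** **Yardstick.** Section 8.1 targets 22.8% × 0.2 = 4.56, given as 4.6 percentage points. The plan states no figure for this subgroup.

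**Step 1: can the planned effect be estimated?** The section 8.3 model is

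change = b0 + b1 × group + b2 × baseline + error.

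Over all NHs the design matrix (intercept, group, baseline) has rank 3 of 3. Among session holders group = 1 for every NH, so the group column equals the intercept column, the rank is 2 of 3, and b1 has no estimate. This needs no assumption about adherence. The SAP's alternatives (robust variance, another GLM, Mann-Whitney) also compare two groups and fail for the same reason.

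**Step 2: could controls enter the subgroup?** The synopsis starts the project in December 2017, so one year later is December 2018, the last month of the first-round follow-up year. If session status were read without a cut-off date, a few controls might qualify. They would be self-selected and almost untreated during follow-up, so they would not rescue the comparison.

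**Step 3: holders against all controls.** Let p be the share of intervention NHs that hold no session. Let d be the difference in mean change between non-holders and holders, after baseline adjustment, had none of them been in the intervention arm. By randomisation the controls have the same expected mix as the whole intervention arm, so

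bias = p × d.

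It favours the intervention if non-holders would have done worse anyway (d > 0) and goes the other way if d < 0. The documents give neither p nor d. Under assumed values:

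- p = 0, any d: bias 0, and the comparison is the intention-to-treat one.
- d = 0, any p: bias 0.
- p = 0.1, d = 3: 0.1 × 3 = 0.3 points; 0.3 / 4.6 = 7% of the target.
- p = 0.2, d = 3: 0.2 × 3 = 0.6 points; 0.6 / 4.6 = 13% of the target.

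**Step 4: simulation check.** No true effect, 31 NHs per group, SD 6.3 and baseline-to-follow-up correlation 0.3 (both from section 8.1), baseline-adjusted regression, independent NHs, 5,000 runs per setting. The assumption varied is r, the correlation between the tendency to hold the session and an otherwise lower follow-up proportion. The direction of the bias is thus built in.

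| Not holding | r = 0 | r = 0.3 | r = 0.5 |
|---|---|---|---|
| 10% | -0.04; 5.3% | -0.29; 5.5% | -0.54; 6.2% |
| 20% | 0.00; 5.3% | -0.57; 6.2% | -0.99; 10.0% |
| 30% | -0.02; 4.9% | -0.85; 8.0% | -1.44; 15.0% |

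Cells show bias in points, then two-sided type I error. With 0% not holding, bias is about 0 and the error about 5%. At r = 0.3 the figures match Step 3 with d near 3: six of 31 NHs not holding gives 0.57 / (6/31) = 2.9. The simulation standard error of a 5% rate is √(0.05 × 0.95 / 5,000) = 0.3 points, so 5.5% cannot be told from 5%.

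**Step 5: what an instrumental estimate would give.** With no controls holding the session, two-stage least squares is essentially the intention-to-treat estimate divided by (1 - p). If the other parts of the intervention have an effect c in NHs that hold no session, then

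ITT / (1 - p) = effect in holders + c × p / (1 - p).

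At p = 0.2 the extra term is 0.25 × c. The standard error is scaled by about 1 / 0.8 = 1.25.

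**The case against.** The strongest reply is that little hangs on this line. The main analysis keeps NHs that hold no session, the SAP states intention to treat, and no primary or co-primary conclusion rests on a subgroup. That stands.

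Second, the problem may never arise. The SAP expects full compliance, section 5.2 requires the agreement of direction, head nurse, physician and pharmacist before enrolment, and section 6.3 withdraws an NH if any of them withdraws consent. With full compliance the substitute comparison is unbiased. This also stands, but the subgroup is then redundant and still has no group effect, and section 8.3.1 itself provides for NHs without a session.

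Third, the baseline-to-12-month change can be described in session holders without any controls, so the line is not wholly unworkable. True, but that is an uncontrolled description, and the planned inferential analyses are all comparisons of two groups.

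A reader might infer that the substitute comparison must favour the intervention. The documents do not show this. Section 5.4 suggests that interested NHs would respond more to the intervention; it does not say how they would have fared without it. Baseline adjustment would also remove any part of the gap that the baseline proportion explains.

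A reader might also infer that an instrumental analysis simply yields the right answer. It does so only if allocation acts through the session alone. Section 5.3 also brings a pharmacist course, a compilation of all NHs' consensus shared with participants, and a deprescribing chapter in the annual report. Each could act where no session was held.

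**Conclusion.** The subgroup analysis fails as written: it has no control arm, and the planned group effect cannot be estimated in it. This follows from the protocol's own text and needs no assumption. Holders against all controls is not a sound replacement. It equals intention to treat under full compliance, and otherwise is open to bias of unknown size and direction if holding relates to prognosis. The illustrative 0 to 0.6 points (0% to 13% of the 4.6-point target) rests wholly on assumed values: 10% to 20% not holding and a gap of 0 to 3 points. Stronger assumptions give more, up to 1.44 points in the simulation with 30% not holding.

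The tempting further step, that the trial's main result is compromised, is not supported, because non-holders stay in the main analysis. The line should be corrected before analysis, but it does not threaten the primary conclusion.

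**What to change.** Remove the session line from the subgroup list in section 8.3.1.

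If an adherence effect is wanted, pre-specify it in both protocol and SAP as a supplementary complier-average analysis of the primary and co-primary outcomes. The SAP does not list the co-primary outcome, so the addition must define it. The specification should contain:

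- two-stage least squares, with allocation as the instrument for holding the session by a stated date within follow-up;
- adjustment for the baseline value of the outcome;
- variance robust to physician clusters, the units that were randomised;
- the assumption that allocation acts only through the session, with a statement that the pharmacist course, the shared consensus compilation and the annual-report chapter may violate it, in which case the session's effect would be overstated;
- timing after the blinded main analysis, because session status identifies the intervention arm.

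Secondary outcomes are best left out: the SAP plans Poisson models with a log link for three of them, and a linear two-stage model is not their counterpart.

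The cost is a wording change in two documents and a little extra analysis. Session status is already visible from the presentation and consensus that section 5.3 requires to be sent to the investigators; only the date must be recorded. The estimate will be less precise than intention to treat, by a factor of about 1 / (1 - p).

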8.3.2 Handling of missing data

Given the nature of the retrospective data collected and the collection mechanisms, we expect that no data will be missing. The supplementary recruitment (see section 8.1, page 17) will ensure that, if any drop-out occurs, the statistical power will remain sufficient to conduct the analyses.

NH with missing drug consumption data will be excluded from all analyses; NH lacking data for one or more of the secondary outcomes will be excluded from this specific analysis.

8.3.3 Ancillary analysis

No ancillary analyses are planned.

8.3.4 Deviations from the original statistical plan

All deviations from the planned analyses will be documented in the final project report, and will be justified.

9. DATA AND QUALITY MANAGEMENT

9.1 Data handling and record keeping / archiving

All documents (agreements to participate, etc.) will be securely archived at the CPC; access to these documents will be restricted to the investigators.

Data from the participating NH and pharmacists will be sent to the investigators via the REDCap instance managed by the PMU; this REDCap instance will also be used for the storage of the raw data. This platform's built-in rights management system and audit trail ensure that only the investigators will have access to the data and that all consultations and modifications are logged. Data will be stored in a coded form; the coding key will be held by the Bureau Qualité Recherche of the PMU, which is not a part of the research project.

Data exported from REDCap for processing and analysis will be stored in a secure location on the PMU infrastructure, accessible only to the investigators.

9.2 Confidentiality, Data Protection

All data collected for this study are strictly confidential and will be accessible to the investigators and their delegates only, in a coded form (no non-coded data will be collected). The EC will have access to all data, including in raw form, for purposes of monitoring, audit and inspection.

After study completion, the results will be published in academic journals (see section 10.1, page 21). Upon request of the editors, processed data will be made available to them; however, no data allowing the identification of the participating NH, partners or residents will be provided.

9.3 Coding

While they are not health-related personal data, data relative to the participating NH will be coded. The coding key will be stored on the PMU secure infrastructure and is not accessible to people outside of the CPC.

9.4 Archiving and destruction

All data will be archived for 10 years after the conclusion of the research project, on the secure infrastructure of the PMU. Raw data will be stored on the REDCap instance, while exported, processed and analysed data will be stored in a secure folder of the IT infrastructure of the PMU. Access will remain exclusive to the investigators through the archival period.

10. PUBLICATION AND DISSEMINATION POLICY

10.1 Publication of results

The results of the effectiveness study will be published in academic journals with the following authorship order:

[name], [name], [name], [name], [name].

The results of the implementation study will be published in academic journals with the following authorship order:

First author to be defined, [name], [name], [name], [name], [name].

In case of other people would significantly contribute to a manuscript, they will be add to those authorship orders.

The results will be presented at academic conferences, as well as in academic, professional and public conferences. Presentations of the results will be organised for the participating NHs.

10.2 Data sharing

The data collected during this research project will not be accessible to third parties.

11. FUNDING AND SUPPORT

This research project is funded by the Swiss National Fund for Scientific Research, through the National research Project 74 "Smarter Health Care" (80%) and by a direct contribution (20%) from the science fund of [name] at the PMU in Lausanne. These funding cover the investigators' salaries and administrative costs. The investigators attest that no conflict of interest exists for this research project.

Participants (pharmacists, physicians and NH personal) from the canton of Vaud will be remunerated for their work in the project through their participation in the cantonal pharmaceutical assistance programme. The remuneration scale for each participant is fixed by the canton. For the remuneration of participants in Fribourg, a grant request has been submitted to the AFIPA-santésuisse joint fund. The remuneration scale will be the same as for the participants in Vaud.

Administrative support in contacting the participants will be provided by the relevant professional associations (AVDEMS, FEDEREMS and SVPh for Vaud, AFIPA/VFA and SPCF for Fribourg).

12. INSURANCE

As this project is outside of HRA's scope, no specific insurance was contracted. All eventual damages are covered by the insurance policies of the PMU.

14. APPENDICES

- Annex 1: Data collected for the implementation study
- Annex 2: Agreement to participate in the study
- Annex 3: QC-DeMo Questionnaire TO Pharmaciens
- Annex 4: QC-DeMo Questionnaire T0 Médecins
- Annex 5: QC-DeMo Questionnaire T0 Infirmiers
- Annex 6: QC-DeMo Questionnaire T3-5 Pharmaciens
- Annexes 7 10: CV of investigators
